Aim 2. Identify theory-based variables (attitudes, self-efficacy, perceived barriers, and social influences related to breast cancer survivorship) that **mediate** the intervention effects of the TICAA on the primary outcomes of the TICAA from baseline to Time Point 1.

Aim 3 (exploratory). Explore whether the effects of the TICAA on the primary outcomes are **moderated** by background factors and disease factors.

Study Design

Organizational structure of the study team:

This is a PI initiated R01 research project that is funded by the National Cancer Institute (National Institute of Health). Due to PI's move from Duke University to Emory University, the study is being transferred from Duke Univ. to Emory University. This is the fourth year of the total 5 year of funding. This IRB approval is needed for the grant transfer.

The study team includes the PI, 1 Co-Investigator, 1 Statistician, multiple Consultants, 3 interventionists and 1 or 2 research assistants. Except the consultants, all research team members will be Emory affiliated. The research team will conduct the study at School of Nursing, Emory University.

Setting and location:

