O Describe any other study-related interactions or interventions: **The Intervention: The**TICAA

This study consists of two groups of research participants: (a) 165 Asian American breast cancer survivors (55 per sub-ethnic group) who do not use the TICAA, but use the information on breast cancer by the American Cancer Society (ACS)(a control group); (b) 165 Asian American breast cancer survivors (55 per sub-ethnic group) who use the TICAA and the information by the ACS (an intervention group). The ACS website includes information on treatment, prevention, genetics, causes, screening, testing, coping, clinical trials, research findings, and statistics related to breast cancer in multiple languages including Mandarin Chinese and Korean. At the completion of the study, both will be allowed to use or continue to use the TICAA.

Theoretical Bases, Information Architecture, and Menus. The TICAA was developed based on the findings from PSs using the information mapping approach.⁶⁹ The TICAA is theoretically based on the Bandura's theory. Based on the Bandura's theory, ^{70–72} most self-management programs include coaching/support and information interventions as part of the program content.⁷³ Likewise, the TICAA includes group and individual (real-time and personalized) coaching/support by health care providers, peer coaching/support, and information to change the women's attitudes, self-efficacy, perceived barriers, and social influences. The TICAA uses a free-form matrix information architecture⁷⁴ and includes menus based on the three components (see below). Graphic User Interface controls⁷⁵ (e.g., push buttons, check boxes, drop-down lists) are used. Presentation styles (e.g., colors, menus, etc.) are tailored based on PSs.

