		Perceived Barriers	Providing information on (examples): - "What breast cancer survivors need to know"/ "Talking about breast cancer and cancer pain"/ "After treatment topics (general and culture-specific)"/ "Grief, mourning, and bereavement"/ "Post trauma stress disorder and breast cancer"
Online Resources	Information	Attitudes/ Self- efficacy/ Perceived Barriers	Culture specific resources (Examples of Korean-specific resources) -Korean cancer society (all about living with cancer)/ Asan medical center (breast cancer)/ Korean breast cancer foundation (breast health) General resources (examples): Patient Summary on Pain by the NCI/ Pain Control: A Guide for Those With Cancer and Their Loved Ones by the American Cancer Society/ Cancer Pain Treatment by International Association for the Study of Pain

Describe processes for translating

The study announcement, informed consent sheet, the TICAA, and Internet survey questionnaires will be available in four languages. Mandarin Chinese, Korean, and Japanese versions have already been prepared using the standard translation and back-translation process by professional translators.

A total of 15 interactive online educational sessions provided to the intervention group are also available in the four languages (already translated using the standard-back translation process^{79,80}).

In addition, messages used in the intervention in other languages will be translated into English, and those in English will be translated into other languages (using both Google translator and daily reviews/corrections by the bilingual interventionists with consultation of professional translators). The interventionists will minimally interfere the interactions among the participants.

o Informed Consent Process:

The participants will be able to consent at any time after reviewing the informed consent sheet on the project website. They are free to go and come back later and consent if needed. Participants

will be informed that their participation is voluntary, and they can withdraw their participation at any time.

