Aim #2: Mediation of Intervention effects. Sequential process random regression growth curve modeling90 will be performed to explore the hypotheses that attitudes, self-efficacy, perceived barriers, and social influences, separately, mediate the relationship between intervention group and change over time in primary outcomes. Specifically, we will examine whether the women who receive the TICAA show more favorable changes on the mediators at post-intervention and the follow-up periods relative to pre-intervention than do those in the control group. Mediational analyses will be performed to examine whether there is statistical support for the view that the putative mediator variables actually mediate effects of the TICAA on participants' needs for

help, physical and psychological symptoms, and quality of life. Although various methods are appropriate for evaluating mediation in this setting, random regression growth curve modeling90 was chosen as it prospectively and longitudinally tests the three criteria of mediation proposed by Baron and Kenny. 91 Modeling will rely on incorporating time varying [mediator] as a predictor of outcome in each sequential assessment. To test the mediation hypothesis, individual slope and intercept parameters will be estimated for each participant based on intervention, mediator, and outcome. The intercept parameters will be coded to represent the value of the linear growth trajectory for each participant at baseline. The sequential process, or lagged approach, will allow for stronger inference regarding causality. Model assumptions will be assessed, and transformations will be applied as necessary. A series of four regressions will be used to test each of the mediational chains according to the criteria specified by Baron and Kenny.91 Significant decreases in outcome will be assessed using the Sobel test. 92

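### Aim 2 tests four mediators one at a time; if they correlate within arm, an inert one can be credited with another's effect, so a joint model should be added

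*Combined protocol and SAP*

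**What the plan says.** In Goals/Aims, Aim 2 is to "Identify theory-based variables" that mediate "the intervention effects of the TICAA on the primary outcomes of the TICAA from baseline to Time Point 1". So the aim is to name variables, not only to show that some mediation occurs.

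Under Plans for analysis, Aim #2, the hypotheses are that "attitudes, self-efficacy, perceived barriers, and social influences, separately, mediate the relationship between intervention group and change over time in primary outcomes". The model is described with one mediator term: "Modeling will rely on incorporating time varying [mediator] as a predictor of outcome in each sequential assessment". The testing procedure is per chain: "A series of four regressions will be used to test each of the mediational chains according to the criteria specified by Baron and Kenny". It ends with "Significant decreases in outcome will be assessed using the Sobel test", which I read as the test of the indirect effect.

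The intervention is built to move all four variables. The section on theoretical bases describes coaching, peer support and "information to change the women's attitudes, self-efficacy, perceived barriers, and social influences". Table 1 assigns the online resources jointly to "Attitudes/ Self- efficacy/ Perceived Barriers".

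The documents give no model with the four mediators together, no correlation between them, no sensitivity analysis for omitted co-mediators, and no alpha or power for Aim 2.

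**The concern.** Randomization protects the path from group to mediator. It does not protect the path from mediator to outcome. If two mediators correlate among women in the same arm and only one affects the outcome, a model holding only the inert one attributes part of the active one's effect to it. The four separate indirect effects then overlap, and their sum can exceed the true total.

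What is at stake is the answer to Aim 2. Separate tests could name several or all of the four variables when only one is at work, and a later revision of TICAA could rest on that. Aim 1 is not affected.

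**Working it through.** **The plan's own figure.** The Recruitment section sizes the trial for Aim 1: 105 per group for 80% power at 0.5 SD and two-sided 0.05/8 = 0.00625. A two-sample t calculation, used as an approximation to the planned Mann-Whitney test, gives 80.4% power at 105. Then 105/(1 − 0.35) = 161.5, so 162 per arm or 324 in all, against 330 planned. For the check below, 330 × 0.65 = 214.5, taken as 214 women.

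**Inputs.**
- From the documents: 330 enrolled; 35% attrition, which the plan states for Time Point 2; four mediators.
- Assumed: each mediator is shifted a = 0.5 SD (borrowed from the plan's outcome effect); one mediator is active with path b = 0.4; the within-arm correlation rho runs from 0 to 0.5; two-sided 0.05; one follow-up; linear models.

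**Formula.** With unit within-arm variances, regressing the outcome on group and one inert mediator gives that mediator a coefficient of rho × b. Its apparent indirect effect is a × rho × b, where the truth is 0. The four separate effects sum to a × b × (1 + 3 rho), where the true total indirect effect is 0.5 × 0.4 = 0.20.

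| rho | Apparent effect, inert mediator | Sum of four (truth 0.20) | Inert declared, separate | Inert declared, joint |
|---|---|---|---|---|
| 0 | 0 | 0.20 | about 2% | about 2% |
| 0.1 | 0.02 | 0.26 | about 4% | about 2% |
| 0.3 | 0.06 | 0.38 | 20–27% | about 2% |
| 0.5 | 0.10 | 0.50 | 58–66% | about 2% |

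The last two columns are simulated rejection rates of the product (Sobel) test for each inert mediator. The ranges cover simulation error and two scalings of the outcome: residual variance 1 (lower end), or total within-arm variance 1, so residual 1 − 0.4² = 0.84 (upper end).

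**Adding the Baron-Kenny total-effect step.** The table leaves out the requirement that group first affects the outcome.
- No direct effect (total 0.20): with residual variance 0.84, each inert mediator is declared in about 8–9% of trials at rho 0.3 and 20–22% at rho 0.5.
- Direct effect 0.3 (total 0.20 + 0.30 = 0.50, the plan's own effect size): about 24–26% and 62–64%.
- With residual variance 1 the figures are somewhat lower: about 6–7% and 17–18% with no direct effect, and about 20% and 54–57% with it.

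**A stricter alpha.** At 0.00625, with b = 0.5, 105 per arm and no total-effect step, each inert mediator is still declared in 5%, 31% and 62% of trials at rho 0.3, 0.5 and 0.7, against 0.0% jointly.

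**What the joint model costs.** With b = 0.3 and 105 per arm, power for the true mediator falls from 91% to 79% at rho 0.5 and from 90% to 59% at rho 0.7.

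**Where the joint model misleads.** Suppose group shifts M1 by 0.5, M1 moves M2 (0.6), and M2 moves the outcome (0.5). M1 truly transmits the effect. The separate model detects it in about 87–92% of trials, the joint model in about 2%.

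**The case against.** - **Shared targeting is not enough.** A reader might infer that inert variables must be credited because TICAA aims at all four, so that Aim 2 cannot succeed. The documents do not support that. Each one-mediator model already conditions on group, and at rho 0 the separate and joint results agree. Within-arm correlation is required, and no figure for it is given. This stands, and the point is conditional on it. Some correlation is nevertheless likely, because use of one program will vary between women. For illustration, if half the arm gained 1 SD on every mediator and half gained nothing, use alone would induce a correlation of 0.25/1.25 = 0.2 in that arm.
- **The total-effect step filters false attributions.** It does when the total effect is small. It does little when the total effect is near the size the trial was planned for.
- **The joint model can be the wrong one.** This stands. A reader might infer that the separate models should be dropped, but they estimate each variable's total indirect effect, including what passes through another mediator. Nothing in the documents establishes that the four act in parallel.
- **The wording is open.** The word separately could describe the hypotheses, which the plan says it will explore, and no sentence bars a joint model. But the single mediator term and the per-chain regressions favor one-at-a-time models, and only Aim 3 is labeled exploratory.
- **The lagged approach helps.** It addresses time order, not omitted co-mediators.
- **The simulation is simplified.** It uses one follow-up and linear regression rather than the planned growth-curve model, and attrition by Time Point 2 although Aim 2 ends at Time Point 1. The rates are therefore illustrative. The mechanism does not depend on these choices.

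**Conclusion.** The point holds in conditional form. As written, Aim 2 has no analysis that separates one mediator from its correlates. At rho 0.1 or below the harm is negligible. From about 0.3 upward, false attribution to an inert variable becomes common under the assumptions used: 20–27% of trials per inert mediator at 0.3 and 58–66% at 0.5, before the total-effect step. After that step the rates depend on the direct effect, and at rho 0.5 they run from roughly 20% to over 60%. The separate models can still show validly whether TICAA changes each variable. What they cannot support alone is the claim that one particular variable mediates independently of the others.

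**What to change.** In the Aim #2 analysis:
1. Keep the four separate models, described as tests of each variable's total indirect effect.
2. Add, for each primary outcome, one model with all four mediators entered together.
3. Report the four specific indirect effects, their sum, and the within-arm correlations between mediators.
4. Claim that a variable mediates independently of the others only from the joint model, and state its assumption that no mediator acts through another.
5. Say that the two sets of results will be read together. A variable that is positive alone but null jointly may be a bystander or may act through another mediator.

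The cost is wording and analysis time, with no new data. There are two downsides: wider intervals from collinearity, and the risk that the joint model misses an upstream mediator, which is why the separate models should stay.

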The participants will be 330 self-reported Asian American women aged 21 years and older who have had a breast cancer diagnosis; can read and write English, Mandarin Chinese, Korean, or Japanese; and have access to the Internet through computers or mobile devices (smart phones and tablets). A total of 210 participants have already been recruited at Duke University and have completed their participation before the PI's move. A total of 120 participants will be newly recruited at Emory University. Those who are in treatment or not in treatment will be included because the TICAA can be used by those in all stages of treatment. A specific fatigue level was not set because compared to those who do not have fatigue or have a low level of fatigue, those with a medium or high levels of fatigue would be more likely to need support through technology-based programs. We excluded those under 21 years old because their cancer experience would be different from adults.' An upper age limit was not set because elderly could be a good target group for technology-based programs because technology-based programs do not require physical

transportation and because women over 75 years old have the highest incidence rate of breast cancer.² Because using more than four languages is infeasible in a study ([name], Personal Communication), and given the diversity of Asian Americans, only four languages including English, Mandarin Chinese, Korean, and Japanese will be used. Mandarin Chinese is a primary language in China, Taiwan, and Hong Kong; Korean is the primary language in South Korea; and Japanese is the primary language in Japan.

o Recruitment:

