The data are mainly collected through the Internet survey questionnaire. When potential participants visit the project Web site (after receiving/reviewing a study announcement), they will be asked to review the informed consent. When participants click I agree to participate, they will have given their consent. Then, after checking them against the inclusion criteria and quota requirements, only those who meet the criteria and requirements will be automatically assigned a serial number, and randomized into two groups using an automated random number generator accessible through the Web site.

Then, the women will be asked to fill out the Internet survey questionnaire (if requested, paper-and-pencil questionnaires will be provided/used, or research staff will assist in administering the Internet surveys over the phone.) and sign up the Web site by creating their own ID and passwords. Whenever they visit the Web site, they need to use the ID and passwords to log in the site. If they want, they can change their ID and passwords. Then, both groups will be provided with an electronic instruction sheet on when they need to come back and fill out additional questionnaires and/or use the program.

Biweekly, the research team will send reminders and thank-you emails. Two weeks before the end of the 1st month, both groups will be asked to fill out the next set of the instruments by the end of the 1st month. Then, 2 weeks before the end of the 3rd month, both groups will be asked to fill out the next set of the instruments by the end of the 3rd month.

O Description of research instruments to be used (e.g., questionnaires, surveys, interview or focus group guides, scales)

Multiple instruments will be used: the Support Care Needs Survey-34 Short Form (SCNS-34SF),⁵⁰ the Memorial Symptom Assessment Scale-Short Form (MSAS-SF),⁵¹ the Functional Assessment of Cancer Therapy Scale-Breast Cancer (FACT-B),⁵² the modified Questions on Attitudes, Self-Efficacy, Perceived Barriers, and Social Influences (QASPS),⁵³ the Cancer Behavior Inventory (CBI),^{54,55,56} the Perceived Isolation Scale (PIS),^{57,58} the Personal Resource Questionnaire (PRQ-2000),⁵⁹ and 27 questions on background characteristics, level of acculturation, and disease factors. The reliability and validity of all the instruments have been established among Asian Americans. Cronbach's alpha of individual instrument ranged from .76 to .96 among Asian Americans.

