Aim #1: Effects on Primary Outcomes. Separate intent-to-treat general linear models 86 will be used to examine differences in continuous outcome measures by intervention group at each time point, adjusting for baseline outcome and any variables that demonstrate imbalances in preliminary analyses. Model assumptions will be assessed, and modifications will be implemented as necessary to improve mode fit. Differences in continuous outcome measures over time will be examined using an intent-to-treat linear mixed-model growth curve analysis with SAS Proc Mixed.86 Mixed models will be used in which all available data collected during follow-up is used.87,88 Separate mixed effects regression models will be generated for each outcome measure. Both random slopes and intercepts will be modeled to represent the subject level deviation from the average, or fixed-effect, slope over time and intercept, respectively. Restricted maximum likelihood estimation will be used, and the most appropriate covariance structure will be examined. The outcomes will be analyzed as repeated observations of the dependent variables, with mean-centered baseline outcome scores serving as a covariate. Other predictors will include intervention group, time from baseline to follow-up, the interaction of group and time, and the interaction of baseline measures and time. Baseline outcome and group will be analyzed as time-independent covariates. Other demographic or treatment timeindependent variables identified in preliminary analyses may be included as covariates. Main effects and higher order interaction terms will be examined. The Akaike information criterion will evaluate overall model fit and to select the best-fitting longitudinal change pattern.89

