Aim #3: Moderation of Intervention Effects. The moderating role of background and disease factors will be generated for each outcome. Intention-to-treat mixed-modeling procedures86 as described above will be used to test and estimate differences in outcome across intervention groups and how moderators modify such differences. Accordingly, coefficient estimates for these measures by time represent the extent to which mediators affect slopes of change for outcome across time. Initial models will include all main effects and possible two- and three-way interactions between moderator, intervention group, and time. With respect to random effects, in addition to random intercepts, random slopes for time, moderator variables will be estimated to account for within-individual variability. As before, each model will control for baseline outcome values, which will be centered about the grand mean for all patients. Accordingly, intercepts represent the mean baseline outcome score across patients, adjusting for all other values included in the respective models.

Training of study team

All research team members will complete CITI training before engaged in the study. Also, to eliminate contamination across interventionists and minimize risk of differential treatment delivery among different interventionists, the interventionists will be trained by the PI with the intervention protocol developed through PSs. The interventionists' first 5 messages through the social media sites and the chat function will be monitored and evaluated by the research team, and the team's feedback will be incorporated into their subsequent coaching/support. Also, the interventionists will learn methods of facilitating discussions without influencing participants and helping women to set goals and solve problems. Two culturally-matched RAs will be trained on the logistics for the participant recruitment, the online survey system, and the delivery of the online questionnaires. Team meetings will be held monthly to address problems, reinforce learning, and monitor progress. Retraining of the interventionists and RAs will be done every 18 months to prevent drift.

Plans for Monitoring the Study for Safety

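### The Aim 2 mediation regressions state no adjustment for common causes of mediator and outcome, and the Aim 1 covariate rule is the wrong criterion to borrow

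*Combined protocol and SAP*

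**What the plan says.** All places are in the combined protocol and SAP.

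- **Aim #2: Mediation of Intervention effects.** The model description is that "individual slope and intercept parameters will be estimated for each participant based on intervention, mediator, and outcome". Each chain then goes through four Baron-Kenny regressions and a Sobel test. No baseline score is named as a covariate, and no background or disease variable is named. The section does not point back to Aim 1. Its stated causal safeguard is the lagged approach, which it says "will allow for stronger inference regarding causality".
- **Aim #1: Effects on Primary Outcomes.** The general linear models are fitted "adjusting for baseline outcome and any variables that demonstrate imbalances in preliminary analyses". For the mixed models, "Other demographic or treatment timeindependent variables identified in preliminary analyses may be included as covariates".
- **Aim #3: Moderation of Intervention Effects.** This section does refer back: mixed models "as described above will be used to test and estimate differences in outcome across intervention groups". It fixes baseline outcome as a covariate.
- **Goals/Aims.** Aim 2 concerns "the intervention effects of the TICAA on the primary outcomes of the TICAA from baseline to Time Point 1", a window with one follow-up. The analysis section also speaks of later follow-up periods.
- **Population to be studied.** "Those who are in treatment or not in treatment will be included".
- **Description of research instruments.** Data collection includes "27 questions on background characteristics, level of acculturation, and disease factors". The items are not listed.

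**The concern.** Randomisation protects the comparison of arms. It does not protect the mediator-to-outcome path, because women are not randomised to levels of self-efficacy, attitudes, barriers or social influences. Within either arm, a woman whose treatment is changing may gain self-efficacy and lose symptoms in the same month without one causing the other. Such a variable can be perfectly balanced between arms and still confound this path, so between-arm imbalance is the wrong trigger for including it. The same holds for baseline scores: if mediator and outcome are already correlated at entry and both persist, they stay correlated at month 1 with no causal link.

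The analysis section asks whether the putative mediators really carry the TICAA's effect. A false chain could send refinement of the program toward the wrong mechanism.

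**Working it through.** **The plan's own figure.** The Recruitment section gives 105 per group for 0.5 SD, 80% power and two-sided alpha 0.05/8 = 0.00625. The normal formula 2(z₀.₉₉₆₈₇₅ + z₀.₈₀)²/0.5² = 2(2.734 + 0.842)²/0.25 = 102.3 gives 103. The t-based version gives 105 (power 80.4%). With 35% attrition, 210/0.65 = 323.1, so 324 are needed, within the planned 330. The figure reproduces. The plan gives no power figure for Aim 2.

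**Inputs.** From the plan: 105 per arm and a 0.5 SD TICAA effect, applied here to both mediator and outcome. Assumed, not in the documents: 20-50% of women on treatment (p); a treatment shift of d = 0.2-0.6 SD in both variables; a baseline to month-1 correlation of r = 0.6; within-arm SD of 1. The true mediator-to-outcome effect is set to zero.

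**Test.** Sobel z = ab/√(a²·se_b² + b²·se_a²) = z_a·z_b/√(z_a² + z_b²), two-sided 5%.

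**Case 1: treatment drives change, baseline scores adjusted.** Given arm and baseline scores, treatment leaves a residual covariance v = d²p(1−p) between mediator and outcome. Each residual variance is R = (1−r²)(1−v) + v, so the spurious partial correlation is v/R. Also z_a = 0.5/√(2R/105). At p = 0.5:

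| d | v | R | v/R | z_a | z_b | Sobel z |
|---|---|---|---|---|---|---|
| 0.2 | 0.010 | 0.644 | 0.016 | 4.52 | 0.22 | 0.22 |
| 0.4 | 0.040 | 0.654 | 0.061 | 4.48 | 0.88 | 0.86 |
| 0.6 | 0.090 | 0.672 | 0.134 | 4.42 | 1.93 | 1.77 |

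Simulated false-positive rates (3,000 replicates per cell) at p = 0.2/0.3/0.5:

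| Scenario | d = 0.2 | d = 0.4 | d = 0.6 |
|---|---|---|---|
| Drives change, baseline scores adjusted | 3.1/3.1/3.2% | 5.3/7.8/8.6% | 15.8/26.7/39.0% |
| Drives change, change scores | 2.8/2.5/2.7% | 3.7/5.2/5.4% | 8.1/15.0/22.9% |
| Difference stable from baseline, baseline scores adjusted | not listed | 2.9/2.4/3.5% | 3.3/3.5/3.9% |

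With no common cause the rate is about 3%, since the Sobel test is conservative here. Independent repeats gave the same pattern, with 15-36% in one set of runs at 0.6 SD. Adding treatment status returns the rate to about 3%, but that is built in, because treatment is the only confounder simulated.

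**Case 2: month-1 mediator to month-3 outcome, also adjusting for month-1 outcome.** If the treatment effect on the outcome holds to month 3, the rates are 3-5% at 0.4 SD and 7-14% at 0.6 SD. If it is still growing, they are 5-8% and 16-34%. If it fades by half, about 3%. So a lag helps in some patterns and not in others.

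**Case 3: no treatment effect, baseline scores left out.** Assume a baseline mediator-outcome correlation ρ of 0.3-0.5.

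- *Simple month-1 regressions.* The spurious partial correlation is r²ρ = 0.36 × 0.3 = 0.108 up to 0.36 × 0.5 = 0.18. With z_a = 0.5/√(2/105) = 3.62 and z_b = 1.56 to 2.63, Sobel z = 1.44 to 2.13. Simulated rates are about 18-56%.
- *Change scores.* The change variance is 2(1−r) = 0.8 and the covariance is ρ(1−r)² = 0.16ρ, so the spurious correlation is 0.2ρ = 0.06 to 0.10. With z_a = 0.5/√(1.6/105) = 4.05 and z_b = 0.87 to 1.45, Sobel z = 0.85 to 1.36. Simulated rates are about 8-20%.
- *Both baseline scores adjusted.* About 3%.

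**Condition.** The TICAA must move the mediator. In a separate run with no effect on the mediator and a strong common cause (0.8 SD), the false rate was 0.2%.

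**The case against.** **The sentence is not a closed list.** It describes which trajectories are estimated, and the Aim 1 mixed-model text allows treatment variables without requiring imbalance. A reader might infer that the plan intends to leave treatment out. The documents do not support that: the covariate set is unstated, not restricted. What stands is that no Aim 2 adjustment is required anywhere, and the rule nearest to hand uses the wrong criterion.

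**The high rates come from a strong case.** They need an equal, same-direction 0.6 SD shift in a month, more than the 0.5 SD assumed for the TICAA, with nothing present at baseline. If half is already present at baseline, the rate is about 5-12%. With a 0.2 SD mediator shift and a 0.6 SD outcome shift it is 4.5-5.8%. With a 0.3 SD TICAA effect on the mediator it is 5.8-12.4%. This stands. A reader might take 15-39% as the expected error of Aim 2, and the documents give no basis for that.

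**The simulated model is not the planned one.** These are two-wave regressions. The plan's participant intercepts are set at baseline and may absorb stable differences and part of the baseline correlation. This stands too, but intercepts do not remove a shared driver of change.

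**Baseline treatment status is an incomplete remedy.** If a quarter of on-treatment women finish during the month and only they shift by 0.6 SD, one run gave 4.6-8.4% unadjusted and 3.6-7.6% adjusted. At 1.0 SD the figures were 11-44% and 8-32%. So adjustment cannot be called a cure, and no document confirms that treatment status was recorded.

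**Aim 2 is framed as exploring hypotheses.** True of the analysis section. The aims, however, label only Aim 3 exploratory, and the analysis section expects causal gain from lagging.

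**Conclusion.** The gap is real and modest. Aim 2 states no adjustment for common causes of mediator and outcome, and balance between arms is not the right test for whether to adjust.

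Treatment as the common cause matters little when the difference is weak (0.2 SD) or stable from baseline. It matters somewhat at 0.4 SD of change in both variables (about 5-9%), and greatly only in the strong 0.6 SD case (about 15-39%). The case for baseline scores is firmer: if mediator and outcome are correlated at 0.3-0.5 at entry, omitting them can by itself give about 18-56% in simple month-1 regressions and 8-20% with change scores. How much of this the planned growth model absorbs cannot be settled from the text.

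Every rate depends on inputs that the documents do not give, and on the TICAA moving the mediator. A reader might extend the point to Aim 1. That does not follow, because the arm contrast is protected by randomisation. The point is worth acting on because the remedy is cheap, not because a false chain has been shown to be likely.

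**What to change.** 1. In every Aim 2 mediator and outcome regression, adjust for baseline mediator and baseline outcome. If the growth model's baseline intercepts are meant to do this, say how.
2. Where the 27 background and disease questions record it, also adjust for baseline on-treatment status, whether or not it differs between arms.
3. State that mediation conclusions assume no remaining mediator-outcome confounding, and name treatment ending during follow-up as an example that baseline status does not capture.

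Reporting the residual mediator-outcome correlation at which each indirect effect becomes zero is optional and descriptive only. In simple linear models it largely restates the mediator-to-outcome path already tested, so it changes no decision.

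The cost is analysis text and code, with no new data. Beyond the baseline outcome that Aim 1 already carries, each regression gains one or two covariates on about 210 women. If treatment status was not recorded for all 330 women, items 1 and 3 still apply. Aim 1 does not change.
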